8.3. Power and Sample Size

8.3.1. Part 1

8.3.1.1. Part 1A

The sample size of this study is driven by safety. Approximately 3000 participants will be randomly assigned in a 2:1 ratio to receive mRNA-1273 and placebo (Section 5.2). With 2000 participants exposed to mRNA-1273, the study has at least 90% probability to observe at least 1 participant with an AE at a true 0.25% AE rate.

Serum samples from all participants will be collected and banked, a subset of participants will be selected, and their samples will be processed for immunogenicity testing (the Immunogenicity Subset).

Approximately 362 participants who receive mRNA-1273 will be selected for the Immunogenicity Subset, with a target of 289 participants receiving mRNA-1273 in the PP Immunogenicity Subset (adjusting for approximately 20% of participants who may be excluded from the PP Immunogenicity Subset, as they may not have immunogenicity results due to any reason). The sample size of the Immunogenicity Subset may be updated with data from other mRNA-1273 studies or external data especially regarding a threshold of protection. In such a situation, the final sample size of the Immunogenicity Subset will be documented in the SAP.

For the primary immunogenicity objective, with approximately 289 participants in the PP Immunogenicity Subset, the study will have > 90% power to rule out 70% with a 2-sided 95% CI for the percentage of mRNA-1273 participants exceeding the acceptable threshold if the true rate of participants exceeding the acceptable threshold is 80%.

If an acceptable Ab threshold of protection against COVID-19 is not available at the time of analysis, for the primary immunogenicity objective, noninferiority tests of 2 null hypotheses based on 2 coprimary endpoints, respectively, will be performed. The sample size calculation for each of the 2 noninferiority tests was performed, and the larger sample size was chosen for the study.

- With approximately 289 participants in the PP Immunogenicity Subset in Study P203 and 289 participants in the PP Immunogenicity Subset in young adults (18 to 25 years of age) from Study P301, there will be 90% power to demonstrate noninferiority of the immune response as measured by Ab GM value in adolescents in Study P203 at a 2-sided α of 0.05, compared with that in young adults (18 to 25 years of age) from Study P301 receiving mRNA-1273, assuming an underlying GMR value of 1 and a noninferiority margin of 1.5. The SD of the log-transformed levels is assumed to be 1.5.
- With approximately 289 participants in the PP Immunogenicity Subset in Study P203 and 289 participants in the PP Immunogenicity Subset in young adults (18 to 25 years of age) from Study P301, there will be at least 90% power to demonstrate noninferiority of the immune response as measured by the SRR in adolescents in Study P203 at a 2-sided α of 0.05, compared with that in young adults (18 to 25 years of age) from Study P301 receiving mRNA-1273, assuming a true SRR of 85% in young adults (18 to 25 years of age) from Study P301, and a true SRR of 85% in adolescents in Study P203 (ie, true rate difference is 0 compared to young adults from Study P301), and a noninferiority margin of 10%.

8.3.1.2. Part 1C

8.3.1.2.1. Part 1C-1– Homologous Booster Phase

All participants enrolled in Part 1A or Part 1B who meet the eligibility criteria for BD will be offered a BD of mRNA-1273 50 μ g. With more than 1,000 participants expected to receive

mRNA-1273 BD, the study Part 1C-1 has a 90% probability to observe at least 1 participant with an AE at a true AE rate of 0.25%.

Serum samples from all participants will be collected and banked, a subset of participants will be selected (as described in the SAP document version 4.0), and their samples will be processed for immunogenicity testing (the Immunogenicity Subset) at specified timepoints.

Approximately 400 participants who receive mRNA-1273 BD will be selected for the Immunogenicity Subset for Part 1C-1, with a target of 289 participants receiving mRNA-1273 BD in the PP Immunogenicity Subset with prebooster negative SARS-CoV-2 for Part 1C-1 (adjusting for approximately 25% of participants who may be excluded as they may have prebooster positive SARS-CoV-2, have no immunogenicity results due to any reason or have protocol deviations impacting critical data).

For the primary immunogenicity objective in Part 1C-1, noninferiority tests of 2 null hypotheses based on 2 coprimary endpoints, respectively, will be performed.

- With approximately 289 participants receiving mRNA-1273 BD in the PP Immunogenicity Subset with prebooster negative SARS-CoV-2 in Study P203 Part 1C-1 and 289 participants in the PP Immunogenicity Subset in young adults (18 to 25 years of age) in Study P301, there will be 90% power to demonstrate noninferiority of the immune response post BD as measured by Ab GM value in adolescents in Study P203 Part 1C-1 compared with Ab GM value in young adults (18 to 25 years of age) following primary series of mRNA-1273 in Study P301, at a 2-sided α of 0.05, assuming an underlying GMR value of 1 and a noninferiority margin of 1.5. The SD of the log-transformed levels is assumed to be 1.5.
- With approximately 289 participants receiving mRNA-1273 BD in the PP Immunogenicity Subset with prebooster negative SARS-CoV-2 in Study P203 Part 1C-1 and 289 participants in the PP Immunogenicity Subset in young adults (18 to 25 years of age) in Study P301, there will be at least 90% power to demonstrate noninferiority of the immune response post BD as measured by SRR in adolescents in Study P203 Part 1C-1 compared with SRR in young adults (18 to 25 years of age) following primary series of mRNA-1273 in Study P301, at a 2-sided α of 0.05, assuming true SRR of 90% in young adults (18 to 25 years of age) following primary series of mRNA-1273 in Study P301, and a true SRR of 90% post BD in adolescents in Study P203 Part 1C-1 (ie, true rate difference is 0 compared to young adults [18 to 25 years of age] from Study P301), and a noninferiority margin of 10%.

8.3.1.2.2. Part 1C-2 – Heterologous Booster Phase

Approximately 362 participants who received non-Moderna COVID-19 vaccine as primary series vaccination at least 3 months prior were planned to be enrolled to receive mRNA-1273 50 μ g as heterologous booster in Part 1C-2. However, the study population in Part 1C-2 will have less than the planned number of participants enrolled, as a result of slow enrollment and discontinuation of recruitment in Part 1C-2 ([Section 3.1.1.4](#)).

8.3.2. Part 2

Approximately 362 participants were planned to be enrolled to receive mRNA-1273 50 µg in the open-label Part 2. However, the study population in Part 2 will have less than the planned number of participants receiving at least one dose of 50 µg mRNA-1273, with a small sample size as a result of slow enrollment and discontinuation of recruitment in Part 2 ([Section 3.1.2](#)).

8.3.3. Part 3

With at least 300 adolescents enrolled in Part 3 to receive 50 µg mRNA-1273.222, the study will have at least a 95% probability to observe at least 1 participant with an AE at a true AE rate of 1%.

Assuming a true serum Ab GMR of 1.6 for GM value against Omicron BA.4/BA.5 at Day 29 after Dose 1 of mRNA-1273.222 in baseline SARS-CoV-2 positive adolescents compared with GM value against Omicron BA.4/BA.5 at Day 57 after Dose 2 of mRNA-1273 primary series in young adults who are baseline SARS-CoV-2 negative in P301, with approximately 168 participants in the PP Immunogenicity Subset who are baseline SARS-CoV-2 positive in P203 Part 3 and 300 young adults in P301 who are baseline SARS-CoV-2 negative, there will be at least >90% power to demonstrate superiority of the serum Ab GM value against Omicron BA.4/BA.5 after Dose 1 of mRNA-1273.222 in adolescents in P203 to that after Dose 2 of mRNA-1273 in young adults in Study P301 at two-sided α of 0.05 using a superiority margin of 1.0. The standard deviation of the natural log transformed levels of Ab is assumed to be 1.5.

Assuming a true serum Ab GMR of 1.1 for GM value against ancestral strain at Day 29 after Dose 1 of mRNA-1273.222 in baseline SARS-CoV-2 positive adolescents compared with GM value against ancestral strain at Day 57 after Dose 2 of mRNA-1273 primary series in young adults who are baseline SARS-CoV-2 negative in P301, this sample size will also provide at least >90% power to demonstrate noninferiority of GM value of Ab against ancestral strain at Day 29 post Dose 1 of mRNA-1273.222 in adolescents in P203 to that after Dose 2 of mRNA-1273 in young adults in Study P301 at two-sided α of 0.05 using a noninferiority margin of 1.5. The standard deviation of the natural log transformed levels of Ab is assumed to be 1.5.

With approximately 30% of participants in Part 3 who may be excluded from the PP Immunogenicity Subset-baseline SARS-CoV-2 positive (PPIS-POS), as they may be baseline SARS-CoV-2 negative or have missing immunogenicity results due to any reason or protocol deviations impacting critical data, approximately 240 participants are required in Part 3 to provide 168 participants in the PP Immunogenicity Subset-baseline SARS-CoV-2 positive.

8.4. Analysis Sets

The analysis sets are defined in [Table 7](#).

Table 7: Analysis Sets

Analysis Set	Description
Randomization Set	All participants who are randomized, regardless of the participants' treatment status in the study.
FAS	All randomized participants who received at least 1 injection of IP.
Immunogenicity Subset	A subset of participants in the FAS will be selected for immunogenicity testing.
PP Immunogenicity Subset	A subset of participants in the FAS will be selected for immunogenicity testing. The PP Immunogenicity Subset includes participants selected for the Immunogenicity Subset who received planned doses of study vaccination per schedule, complied with immunogenicity testing schedule, and have no major protocol deviations that impact key or critical data. Participants who are seropositive at baseline will be excluded from the PP Immunogenicity Subset. The PP Immunogenicity Subset will be used for analyses of immunogenicity unless specified otherwise.
PP Set for Efficacy	All participants in the FAS who received planned doses of study vaccination, had no immunologic or virologic evidence of prior COVID-19, and have no major protocol deviations that impact key or critical efficacy data.
Solicited Safety Set	The Solicited Safety Set consists of FAS participants who contributed any solicited AR data. The Solicited Safety Set will be used for the analyses of solicited ARs.
Safety Set	All randomized participants who receive at least 1 dose of IP. The Safety Set will be used for all analyses of safety except for the solicited ARs.
mITT Set	All participants in the FAS who have no serologic or virologic evidence of prior SARS-CoV-2 infection before the first dose of IP (both negative RT-PCR test for SARS-CoV-2 and negative serology test based on bAb specific to SARS-CoV-2 nucleocapsid) at baseline.
mITT1 Set	All participants in the mITT Set excluding those who received the wrong treatment (ie, at least 1 dose received is not as randomized or planned).
PP Immunogenicity Subset for BD phase	The PP Immunogenicity Subset for BD phase includes participants who received planned BD per schedule, complied with immunogenicity testing schedule, and have no major protocol deviations that impact key or critical data, with prebooster negative or positive SARS-CoV-2. The PP Immunogenicity Subset with prebooster negative SARS-CoV-2 will be used for the primary immunogenicity analysis.
PP Immunogenicity Subset for Part 3	The PP Immunogenicity Subset for Part 3 includes participants who received planned dose per schedule, complied with immunogenicity testing schedule, and have no major protocol deviations that impact key or critical data, with baseline negative or positive SARS-CoV-2. The PP Immunogenicity Subset for Part 3 with baseline-positive SARS-CoV-2 status will serve as the population for the primary and secondary analysis of immunogenicity data at Day 29 in Part 3.

Abbreviations: AR = adverse reaction; bAb = binding antibody; COVID-19 = coronavirus disease 2019; FAS = full analysis set; IP = investigational product; mITT = modified intent-to-treat; PP = per-protocol; RT-PCR = reverse transcription polymerase chain reaction; SARS-CoV-2 = Severe Acute Respiratory Syndrome coronavirus 2.

Note: Positive SARS-CoV-2 status at baseline is defined as a positive RT-PCR test for SARS-CoV-2, and/or a positive serology test based on bAb specific to SARS-CoV-2 nucleocapsid (as measured by Roche Elecsys Anti-SARS-CoV-2 assay) on or before Day 1. Negative status is defined as a negative RT-PCR test for SARS-CoV-2, and a negative serology test based on bAb specific to SARS-CoV-2 nucleocapsid (as measured by Roche Elecsys Anti-SARS-CoV-2 assay) on or before Day 1.

8.5. Statistical Methods

Data from Part 1A, Part 1B, and Part 1C will be presented separately as applicable.

8.5.1. Baseline Characteristics and Demographics

Demographic variables (eg, age, race, sex, height, weight, and BMI) and baseline characteristics will be summarized by treatment group. Summary statistics (mean, SD for continuous variables, and number and percentage for categorical variables) will be provided.

8.5.2. Safety Analyses

All safety analyses will be based on the Safety Set, except summaries of solicited ARs, which will be based on the Solicited Safety Set. All safety analyses will be provided by treatment group.

Safety and reactogenicity will be assessed by clinical review of all relevant parameters including solicited ARs (local and systemic events), unsolicited AEs, SAEs, MAAEs, AESI, AEs leading to discontinuation, vital sign measurements, and physical examination findings.

The number and percentage of participants with any solicited local AR, with any solicited systemic AR, and with any solicited AR during the 7-day follow-up period after each injection (except Part 1B) will be summarized.

The number and percentage of participants with any solicited local AR, with any solicited systemic AR, and with any solicited AR during the 7-day follow-up period after each dose (except Part 1B) will be provided. A 2-sided 95% exact CI using the Clopper-Pearson method will also be provided for the percentage of participants with any solicited AR.

The number and percentage of participants with unsolicited AEs, SAEs, MAAEs, Grade 3 or higher ARs and AEs, and AEs leading to discontinuation from IP or withdrawal from the study will be summarized. Unsolicited AEs will be presented by MedDRA preferred term and system organ class.

The number of events of solicited ARs, unsolicited AEs/SAEs, and MAAEs will be reported in summary tables accordingly.

For all other safety parameters, descriptive summary statistics will be provided, and [Table 8](#) summarizes analysis strategy for safety parameters. Further details will be described in the SAP.

Table 8: Analysis Strategy for Safety Parameters

Safety Endpoint	Number and Percentage of Participants, Number of Events	95% CI
Any solicited AR (overall and by local, systemic)	X	X
Any unsolicited AE	X	—
Any SAE	X	—
Any AESI	X	—
Any unsolicited MAAE	X	—
Any unsolicited treatment-related AE	X	—

Safety Endpoint	Number and Percentage of Participants, Number of Events	95% CI
Any treatment-related SAE	X	—
Discontinuation from dosing/withdrawal from study participation due to AE	X	—
Any severe AE	X	—
Any treatment-related severe AE	X	—

Abbreviations: AE = adverse event; AESI = adverse event of special interest; AR = adverse reaction; CI = confidence interval; MAAE = medically attended adverse event; PT = preferred term; SAE = serious adverse event; SOC = system organ class.

Notes: 95% CI using the Clopper-Pearson method, X = results will be provided. Unsolicited AEs will be summarized by SOC and PT coded by MedDRA.

8.5.3. Immunogenicity Analyses in Part 1

The SAP will describe the complete set of immunogenicity analyses, including the approach to sample participants into an Immunogenicity Subset for analysis of immunogenicity. The PP Immunogenicity Subset is the primary analysis set for immunogenicity unless otherwise specified. The primary immunogenicity objective of this study is to use the immunogenicity response to infer efficacy in adolescents (12 to <18 years in this study). The primary immunogenicity analysis is performed in Part 1A.

If an accepted serum Ab threshold of protection against COVID-19 is available based on data from other mRNA-1273 studies or external data, the number and percentage of participants with Ab greater than or equal to the threshold at Day 57 will be provided with a 2-sided 95% CI using the Clopper-Pearson method. If the lower bound of the 95% CI on the mRNA-1273 group is >70%, the primary immunogenicity objective of this study will be considered to be met.

The percentage of participants with serum Ab greater than or equal to the threshold with 95% CI will be provided at each postbaseline timepoint. The CI will be calculated using the Clopper-Pearson method.

If an accepted serum Ab threshold of protection against COVID-19 is not established, the noninferiority of primary vaccine response as measured by Ab GM value and SRR in adolescents compared with those in young adults (18 to 25 years of age) receiving mRNA-1273 will be assessed. The study is considered as meeting the primary immunogenicity objective if the noninferiority of the immune response to mRNA-1273 as measured by both GM value and SRR at Day 57 is demonstrated in adolescents in this study at a 2-sided α of 0.05, compared with that in young adults (18 to 25 years of age) in Study P301 receiving mRNA-1273.

An ANCOVA model will be carried out with Ab value at Day 57 as a dependent variable and a group variable (adolescents in Study P203 and young adults in Study P301) as the fixed variable. The GM values of the adolescents at Day 57 will be estimated by the GLSM from the model. The GMR (ratio of GM values) will be estimated by the ratio of GLSM from the model. A corresponding 2-sided 95% CI will be provided to assess the difference in immune response for the adolescents in Study P203 compared to the young adults (18 to 25 years of age) in Study P301 at Day 57. The noninferiority of immune response to mRNA-1273 as measured by GM value will be considered demonstrated if the lower bound of the 95% CI of the GMR is >0.667 based on the noninferiority margin of 1.5.

The number and percentage (rate) of participants achieving Ab seroresponse at Day 57 will be summarized. The difference of SRRs between adolescents receiving mRNA-1273 in Study P203 and young adults (18 to 25 years of age) receiving mRNA-1273 in Study P301 will be calculated with 95% CI. The noninferiority in SRR of adolescents in Study P203 compared to young adults (18 to 25 years of age) in Study P301 will be considered demonstrated if the lower bound of the 95% CI of the SRR difference is >-10%, based on the noninferiority margin of 10%.

In addition, the GM level of specific nAb and bAb with corresponding 95% CI will be provided at each timepoint. The 95% CIs will be calculated based on the t-distribution of the log transformed values then back transformed to the original scale. The GMFR of nAb and bAb with corresponding 95% CI will be provided at each timepoint with Day 57 as the primary timepoint of interest. Descriptive summary statistics including median, minimum, and maximum will also be provided.

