2. OBJECTIVES AND ENDPOINTS

The objectives which will be evaluated in this study and endpoints associated with each objective are provided in [Table 1](#), [Table 2](#), and [Table 3](#).

Table 1: Part 1 Study Objectives and Endpoints

Objectives	Endpoints
Primary Objectives	Primary Endpoints

 To evaluate the safety and reactogenicity of 100 µg mRNA-1273 vaccine administered in 2 doses 28 days apart 	
 Solicited local and systemic ARs through 7 days after each injection Unsolicited AEs through 28 days after each injection MAAEs through the entire study period SAEs through the entire study period AESIs through the entire study period Vital sign measurements Physical examination findings

 To infer efficacy of mRNA-1273 (100 µg, 2 doses 28 days apart), serum Ab responses obtained 28 days after the second injection of mRNA-1273 (Day 57) will be either: 
 Evaluated against an accepted Ab threshold of protection against COVID-19 (if established in Study P301) Compared in primary vaccine response as measured by GM values of serum Ab and SRR in Study P203 with those obtained from young adult recipients (18 to 25 years of age) of mRNA-1273 in the clinical endpoint efficacy trial (Study P301) 	
 The proportion of participants with a serum Ab level at Day 57 \geq an Ab threshold of protection¹ The primary vaccine response as measured by GM value of serum Ab level and SRR from Study P203 vaccine recipients at Day 57 compared with those obtained from young adult recipients (18 to 25 years of age) at Day 57 in the clinical endpoint efficacy trial (Study P301)² 
 If an accepted serum Ab threshold of vaccine protection against COVID-19 is available, this analysis will form the basis to infer efficacy If a threshold is not available, efficacy will be inferred based on establishing noninferiority of adolescent (12 to < 18 years; this clinical study) to adult GM values of serum Ab and SRR obtained in Study P301 (GM value 12 to < 18 years / GM value 18 to 25 years)
Secondary Objectives	Secondary Endpoints

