7.5. Safety Definitions and Related Procedures

7.5.1. Adverse Event

An AE is defined as any untoward medical occurrence associated with the use of a drug in humans, whether or not considered drug related.

Events Meeting the Adverse Event Definition

- Exacerbation of a chronic or intermittent pre-existing condition including either an increase in frequency and/or intensity of the condition
- New conditions detected or diagnosed after the first dose of IP even though they may have been present before the start of the study

Events NOT Meeting the Adverse Event Definition

- Medical or surgical procedure (eg, endoscopy, appendectomy): the condition that leads to the procedure should be the AE.
- Situations in which an untoward medical occurrence did not occur (social and/or convenience admission to a hospital).

An AR is any AE for which there is a reasonable possibility that the vaccine caused the AE ([Section 7.5.9](#)). For the purposes of investigational new drug safety reporting, “reasonable possibility” means that there is evidence to suggest a causal relationship between the vaccine and the AE.

An unsolicited AE is any AE reported by the participant that is not specified as a solicited AR in the protocol or is specified as a solicited AR but starts outside the protocol-defined period for reporting solicited ARs (ie, for the 7 days after each dose of vaccine).

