Medical judgment should be exercised in deciding whether SAE reporting is appropriate in other situations, such as important medical events that may not be immediately life-threatening or result in death or hospitalization but may jeopardize the participant or require medical or surgical intervention to prevent one of the other outcomes listed in the above definition. These events should usually be considered serious. Examples of such medical events include allergic bronchospasm requiring intensive treatment in an emergency room or at home, blood dyscrasias or convulsions that do not result in inpatient hospitalization, or the development of drug dependency or drug abuse.

7.5.3. **Solicited Adverse Reactions**

The term “reactogenicity” refers to the occurrence and intensity of selected signs and symptoms (ARs) occurring after IP injection. The eDiary will solicit daily participant reporting of ARs using a structured checklist ([Section 7.1.1](#)). Participants will record such occurrences in an eDiary on the day of each dose injection and for the 6 days after the day of dosing (Part 1A, Part 1C, Part 2, and Part 3 only).

Severity grading of reactogenicity will occur automatically based on participant entry into the eDiary according to the grading scales presented in [Table 6](#) modified from the Toxicity Grading Scale for Healthy Adult and Adolescent Volunteers Enrolled in Preventative Vaccine Clinical Trials ([DHHS 2007](#)).

If a solicited local or systemic AR continues beyond Day 7 after vaccination, the participant will be prompted to capture details of the solicited local or systemic AR in the eDiary until it resolves or the next IP injection occurs whichever occurs first; capture of details of ARs in the eDiary should not exceed 28 days after each vaccination. ARs recorded in the eDiary beyond Day 7 should be reviewed by the study site staff either during the next scheduled telephone call or at the next study site visit. All solicited ARs (local and systemic) will be considered causally related to dosing.

Table 6: Solicited Adverse Reactions and Grades

Reaction	Grade 0	Grade 1	Grade 2	Grade 3	Grade 4^a
Injection site pain	None	Does not interfere with activity	Repeated use of over-the-counter pain reliever > 24 hours or interferes with activity	Any use of prescription pain reliever or prevents daily activity	Requires emergency room visit or hospitalization

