Any solicited AR that meets any of the following criteria must be entered into the participant's source document and must also be recorded by the study site staff on the solicited AR page of the participant's eCRF:

- Solicited local or systemic AR that results in a visit to an HCP; otherwise meets the definition of a MAAE
- Solicited local or systemic AR leading to the participant withdrawing from the study or the participant being withdrawn from the study by the investigator (AE leading to withdrawal)
- Solicited local or systemic AR lasting beyond 7 days after injection
- Solicited local or systemic AR that leads to participant withdrawal from IP
- Solicited local or systemic AR that otherwise meets the definition of an SAE

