7.5.4. Medically Attended Adverse Events

A MAAE is an AE that leads to an unscheduled visit to an HCP. This would include visits to a study site for unscheduled assessments (eg, abnormal laboratory test results follow-up, COVID-19 [Section 7.4.1]) and visits to HCPs external to the study site (eg, urgent care, primary care physician). Investigators will review unsolicited AEs for the occurrence of any MAAE. Unsolicited AEs will be captured on the AE page of the eCRF.

All confirmed symptomatic COVID-19 cases (Section 7.4.1) will be recorded as MAAEs and reported to the Sponsor or designee immediately and in all circumstances within 24 hours, using the SAE Mailbox, the SAE Hotline, or the SAE Fax line (Section 7.5.11). The investigator will submit any updated COVID-19 case data to the Sponsor within 24 hours of it being available.

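### Table 8 counts only unsolicited MAAEs, although the primary safety endpoint and Sections 7.5.3 and 7.5.4 also cover solicited reactions that lead to a healthcare visit

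*Protocol*

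**What the plan says.** **Endpoint.** Protocol Section 2 lists "MAAEs through the entire study period" as a primary safety endpoint for Part 1 (Table 1). The same entry recurs for Parts 1C-1, 1C-2, 2 (Table 2) and 3 (Table 3). None of these entries is limited to unsolicited events.

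**Definition.** Section 7.5.4: "A MAAE is an AE that leads to an unscheduled visit to an HCP". Solicited reactions are not excepted.

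**Solicited reactions.** Section 7.5.3 lists the solicited reactions that must go into the source document and onto the solicited AR page of the eCRF. One item is: "Solicited local or systemic AR that results in a visit to an HCP; otherwise meets the definition of a MAAE". The same section states: "All solicited ARs (local and systemic) will be considered causally related to dosing".

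**Unsolicited events.** Section 7.5.1: "An unsolicited AE is any AE reported by the participant that is not specified as a solicited AR in the protocol". A listed term counts as unsolicited only if it starts outside the 7-day solicited window.

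**Identification.** Section 7.5.4: "Investigators will review unsolicited AEs for the occurrence of any MAAE". It mentions no corresponding review of solicited reactions.

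**Planned counts.** The MAAE row of Table 8 (Section 8.5.2) reads "Any unsolicited MAAE". The rows for SAEs, AESIs and severe AEs carry no such qualifier. Section 8.5.5 names MAAEs, in parentheses, as one kind of unsolicited AE. The running text of Section 8.5.2 instead plans "The number and percentage of participants with unsolicited AEs, SAEs, MAAEs, Grade 3 or higher ARs and AEs", and a later sentence lists MAAE events as an item separate from unsolicited AEs and SAEs. Sections 8.5.6.1, 8.5.6.2, 8.5.7 and 8.5.8 also list MAAEs without a qualifier of their own.

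**The concern.** The counting rule in Table 8 is narrower than the endpoint it serves. Take a participant with fever on Day 2 who is seen at urgent care. By Sections 7.5.3 and 7.5.4 this is a MAAE. By Section 7.5.1 it is not an unsolicited AE, because fever is a solicited term and began inside the window. It therefore falls outside the one MAAE row that Table 8 provides.

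The protocol foresees such events. In Table 6, Grade 4 is defined by an emergency room visit or hospitalization for eight solicited reactions: injection site pain, axillary swelling or tenderness, headache, fatigue, myalgia, arthralgia, nausea/vomiting and chills. Grade 3 nausea/vomiting mentions outpatient intravenous hydration, and Grade 3 chills mentions medical intervention.

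What is at stake is the meaning of a primary safety endpoint. The events left out are all deemed related to dosing. They belong to a class that Section 1.2.2.5 reports as more common in the mRNA-1273 group, and more often Grade 3 or higher there than with placebo. Two analysts working from this protocol could produce different MAAE tables, each with textual support.

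**Working it through.** This is mainly a comparison of texts. The protocol gives no planned MAAE rate to reproduce.

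**Step 1. Is an attended solicited reaction a MAAE?** Yes. The Section 7.5.4 definition covers any AE with an unscheduled healthcare visit, and Section 7.5.3 names this case.

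**Step 2. Can it also be an unsolicited AE?** Not if it is a listed term starting within 7 days of a dose (Section 7.5.1).

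**Step 3. Which planned summaries include it?**

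| Place | Attended solicited reaction counted as a MAAE? |
|---|---|
| Section 2 endpoint | Yes |
| Sections 7.5.3 and 7.5.4, definition | Yes |
| Section 7.5.4, identification sentence | Not mentioned |
| Section 8.5.2, running text | Yes, on its natural reading |
| Section 8.5.2, Table 8 | No |
| Section 8.5.5 | No, as worded |
| Sections 8.5.6.1, 8.5.6.2, 8.5.7, 8.5.8 | No limit stated |

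The natural reading of the running text is the unrestricted one. The word unsolicited cannot sensibly govern the whole list, because the list goes on to include ARs graded 3 or higher.

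**Step 4. Direction.** Leaving out events that meet the definition can lower the MAAE count but never raise it.

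**Step 5. Size.** The published interim figures in Section 1.2.2.5 reproduce: 1002/2577 = 38.9% with any MAAE, and 26/2577 = 1.0% with a MAAE considered related. Neither gives the size of the gap. The protocol does not say how many solicited reactions led to a visit, or whether these two counts include them.

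For scale only, let r be the share of participants whose sole MAAE is an attended solicited reaction. Table 8 then understates the MAAE percentage by r percentage points. If r is assumed to lie between 0.1% and 1% in the planned Part 1A vaccine arm of 2000 (Section 8.3.1.1), the shortfall is 0.001 × 2000 = 2 to 0.01 × 2000 = 20 participants. The range for r is an assumption with no source in the protocol.

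**The case against.** The strongest reply is that one row label is being read as a settled exclusion. Section 8.5.2 plans MAAE summaries in its text without the restriction, the part-specific sections do the same, and details are left to the SAP, which is not available here. This stands in part: the protocol does not consistently exclude these events. But the narrow wording is not an isolated slip. Section 8.5.5 repeats it, and within Table 8 the qualifier is attached to MAAEs while the rows for SAEs, AESIs and severe AEs have none. A SAP that has to follow both the text and the table starts from a contradiction.

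Second, the events are not lost. They count as any solicited AR, with a Clopper-Pearson interval, and among ARs graded 3 or higher where that applies. They also fall in the SAE, AESI, severe AE or discontinuation rows if they qualify. This stands fully. What those rows do not show is that the reaction led to medical care, which is what a MAAE endpoint measures.

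Third, Section 7.5.4 does not say that only unsolicited AEs are reviewed, and Section 7.5.3 requires attended solicited reactions on the eCRF. This also stands: the weakness is in tabulation, not in collection.

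A reader might go further and infer that a planned count of related MAAEs will lose vaccine-caused events. The documents do not support that. Table 8 has no related-MAAE row; such a count appears only as an interim result in Section 1.2.2.5, and its composition is not stated. Nor can the missing fraction be estimated from the 26 of 2577. Besides the unknown rate and composition, the data cut behind that denominator covers blinded and open-label phases, and solicited reactions were not collected in Part 1B (Sections 7.1.1 and 7.5.7).

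**Conclusion.** The point holds as an inconsistency between a primary safety endpoint and the count planned for it. If Table 8 is followed, attended solicited reactions are reported as solicited ARs but not as MAAEs, and the MAAE count can be understated.

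In Part 1A, the only part with a placebo arm, the understatement would be larger in the vaccine arm, provided that attended reactions follow the reported pattern of solicited reactions overall. The protocol does not give the figures to confirm that.

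The size cannot be computed from the protocol. A reader might infer that the MAAE results are biased in favor of the vaccine. The documents support only that they can be understated if the narrow row is used. MAAE summaries are descriptive, with no hypothesis test or success criterion attached, so the immunogenicity conclusions are untouched. The change is still worth making, because it affects a reported primary safety count and the required data are already collected.

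**What to change.** Preferred change: relabel the Table 8 row as *Any MAAE (solicited AR or unsolicited AE leading to an unscheduled HCP visit)* and keep *unsolicited MAAE* as a sub-row. Draw the solicited component from the solicited AR page of the eCRF, which Section 7.5.3 already requires. In Section 7.5.4, state that solicited ARs are reviewed for MAAEs as well. In Section 8.5.5, remove the wording that makes MAAEs a subset of unsolicited AEs. State that the combined row uses the Safety Set, since solicited AR summaries use the Solicited Safety Set.

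Alternative, if only unsolicited MAAEs are meant: say so in the Section 2 endpoints and in the running text of Sections 8.5.2 and 8.5.6 to 8.5.8, and add a separate row for solicited ARs that led to an HCP visit.

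The cost is a few lines of wording and one merge of two eCRF pages at analysis. No new data collection is needed.
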